^d Taken following progression on the latest line of therapy. The collection of this tumour tissue sample for central mutation analysis is not included in the 28-day screening period.

^e The optional second tumour tissue sample can be taken as part of the same procedure as the mandatory screening biopsy for mutation analysis.

^f Archival tumour sample only to be submitted after T790M positive status confirmed by central testing. Not required for T790M negative patients.

^g To be completed pre-dose.

^h If screening assessments are not done at Visit 2, but have been done at Visit 1 and have been performed within 14 days window prior to starting study treatment, with no change in condition and no clinical indication to do so, they do not have to be repeated on Visit 2 if subject's condition has not changed. (except for fasting glucose).

ⁱ To be taken at the same time as the screening biopsy is taken or prior to mutation screening. All plasma samples are required by AstraZeneca, regardless of the outcome of the mutation screening.

^j Collect every 6 weeks up to and including progression (corresponding with the RECIST assessments – and continuing after treatment discontinuation in absence of disease progression).

^k If for any reason the sample is not drawn prior to first dose it may be taken at any visit until the last study visit.

^l To be obtained at one time point at any time from Cycle 2 Day 1 onwards

^m If only one measurable lesion exists, it is acceptable to be used as long as it has not been previously irradiated, and baseline tumour assessment scans are done at least 14 days after the screening biopsy is performed.

ⁿ Assess every 6 weeks relative to first dose until end of study (including survival follow-up period) and at the time of progression.

^o Assess every 3 weeks relative to first dose until end of study (including survival follow-up period) and at the time of progression.

^p PRO-CTCAE will only be administered in those countries where a linguistically validated version exists.

^q Assessed at Cycle 7 Day 1 then every 3 weeks relative to first dose thereafter until end of study (including survival follow-up period) and at the time of progression.

^r Following AZD9291 discontinuation, SAEs considered related to study procedures should continue as outlined in Table 6.

^s Survival status including anti-cancer treatment to be performed every 6 weeks (relative to first dose) following disease progression or withdrawal from treatment.

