4.3.4 Survival follow-up

- Assessments for survival should be made every 6 weeks (relative to first dose) following objective disease progression or withdrawal from treatment. Survival information may be obtained via telephone contact with the patient, patient's family or by contact with the patient's current physician. In addition to the survival status, the following assessments are also required post progression as detailed in the study plan (see [Table 1](#) and [Table 2](#)):
- EORTC QLQ-C30 and EQ-5D-5L every 6 weeks.
- EORTC QLQ LC13 and PRO-CTCAE every 3 weeks.
- Anti-cancer therapy collected every 6 weeks.
- Subsequent response/progression data every 6 weeks until the first confirmed disease progression on a subsequent treatment.

Survival data will be collected up to the time of the final OS analysis. Patients should be contacted in the 2 weeks following the data cut-off for the final survival analyses to provide complete survival data.

The status of ongoing, withdrawn (from the study) and "lost to follow-up" patients at the time of an overall survival analysis should be obtained by the site personnel by checking the patients notes, hospital records, contacting the patients general practitioner and checking publicly available death registries. In the event that the patient has actively withdrawn consent to the processing of their personal data, the vital status of the patient can be obtained by site personnel from publicly available resources where it is possible to do so under applicable local laws.

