ORR rate is defined as the number (%) of subjects with measurable disease with at least one visit response of CR or PR that is confirmed at least 4 weeks later (according to ICR for the primary analysis). Data obtained up until progression, or last evaluable assessment in the absence of progression, will be included in the assessment of RR. However, any complete response or partial response which occurred after a further anticancer therapy was received will not be included in numerator of the ORR calculation.

In the case where a subject has two non-consecutive visit responses of PR, then, as long as the time between the 2 visits of PR is greater than 4 weeks and there is no PD between the PR visits, the subject will be defined as a responder. Similarly, if a subject has visit responses of CR, NE, CR, then, as long as the time between the 2 visits of CR is greater than 4 weeks, then a best response of CR will be assigned.

Duration of Response (DoR)

Duration of response will be defined as the time from the date of first documented response, (that is subsequently confirmed) until date of documented progression or death in the absence of disease progression, the end of response should coincide with the date of progression or death from any cause used for the PFS endpoint. The time of the initial response will be defined as the latest of the dates contributing towards the first visit response of PR or CR. If the response is not confirmed, it will not be included.

If a subject does not progress following a response, then their duration of response will use the PFS censoring time.

Disease control rate (DCR)

Disease control rate is defined as the percentage of patients who have a BoR of CR or PR or SD.

Tumour Shrinkage

Tumour shrinkage will be assessed using RECIST tumour response. The absolute change and percentage change from baseline in sum of tumour size at each assessment will be calculated. The best change in tumour size will include all assessments prior to progression or start of subsequent anti-cancer therapy.

Progression Free Survival (PFS)

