For each of the symptoms scales/items in QLQ LC13, time to symptom deterioration will be defined as the time from enrolment until the date of first clinically meaningful symptom deterioration (an increase in the score from baseline of ≥ 5) or death (by any cause) in the absence of a clinically meaningful symptom deterioration, regardless of whether the patient withdraws from study therapy or receives another anticancer therapy prior to symptom deterioration. Death will be included as an event only if the death occurs within two visits of the last PRO assessment where the symptom change could be evaluated.

Patients whose symptoms (as measured by QLQ LC13) have not shown a clinically meaningful deterioration and who are alive at the time of the analysis will be censored at the time of their last PRO assessment where the symptom could be evaluated. Also, if symptoms progress after two or more missed PRO assessments or the patient dies after two or more missed PRO assessments, the patient will be censored at the time of the last PRO assessment where the symptom could be evaluated. If a patient has no evaluable assessments or does not have baseline data they will be censored at day 1. The population for analysis of time to symptom deterioration will include a subset of the FAS population who have baseline scores ≤ 95 .

Symptom Improvement Rate

The symptom improvement rate will be defined as the number (%) of patients with two assessments at least 18 days apart (ie, 21 days allowing a visit window of 3 days) which showed a clinically meaningful improvement (a decrease from baseline score > 5 for LC13 scales/items or > 10 for C30 scales/items) in that symptom from baseline. The denominator

will consist of a subset of the FAS population who have a baseline symptom score ≥ 5 (LC13 scales/items) or ≥ 10 (C30 scales/items).

Time from enrolment to second progression (PFS2) (exploratory)

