PFS will be displayed using a Kaplan-Meier plot. The number events, median (calculated from the Kaplan Meier plot), and the proportion of patients without an event at 6, 12, 18 and 24 months summarised. PFS will be presented based on the ICR assessments, and as a sensitivity analysis PFS will be presented based on the investigator assessment.

Overall Survival (OS)

When there is sufficient data (>20 events), OS will be displayed using a Kaplan-Meier plot. The number events, median (calculated from the Kaplan Meier plot), and the proportion of patients without an event at 6, 12 and 18 months will be summarised.

As appropriate, summaries of the number and percentage of patients who have died, are still in survival follow-up, are lost to follow-up and have withdrawn consent will be presented.

HRQoL and symptoms

Time to symptom deterioration

For each of the 6 symptoms scales/items in QLQ LC13 (dyspnoea, cough, haemoptysis, chest pain, arm/shoulder pain, other pain) time to deterioration in symptoms will be presented using a Kaplan-Meier plot. Summaries of the number and percentage of subjects experiencing a clinically meaningful deterioration or death, and the median time to deterioration will be also be provided. The proportion of patients alive and free from symptom deterioration at 3, 6, 12 and 24 months will be summarized using the Kaplan-Meier estimates.

Symptom Improvement Rate

For each of the symptom scales/items in QLQ LC13, a 95% confidence interval for symptom improvement rate will be constructed using the Newcombe-Wilson method. In addition, the change from baseline at each assessment time point (in terms of proportion of patients improved, stable, and worsened as defined in Section 8.4) and the mean change from baseline scores at each time point will be summarised for all symptom scales/items from the QLQ LC13 and QLQ-C30.

Definition of clinically meaningful changes

For each functional scale in the QLQ-C30 (physical, role, emotional, cognitive, social) and for Global Health status, the change from baseline at each assessment time point (in terms of proportion of patients improved, stable, and worsened as defined in Section 8.4) and the mean change from baseline scores at each time point will be summarised.

Safety Assessments

Safety and tolerability data will be presented using summaries and descriptive statistics, as detailed in the SAP.

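### The symptom improvement rate has no cut at subsequent anti-cancer therapy, so improvement on a later drug can only raise the rate attributed to AZD9291

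*Protocol*

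**What the plan says.** The definition is in protocol section 8.4, Symptom Improvement Rate: "The symptom improvement rate will be defined as the number (%) of patients with two assessments at least 18 days apart", with improvement of more than 5 points on LC13 scales or more than 10 on QLQ-C30 scales. The denominator is the subset of the full analysis set whose baseline score is high enough to allow improvement. No limit is set at the end of AZD9291, at progression or at the next therapy. Section 8.7.2 gives a 95% confidence interval for the LC13 rates and adds no limit.

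Collection runs well past the end of treatment. For LC13, a footnote to Table 1 (section 4) says: "Assess every 3 weeks relative to first dose until end of study (including survival follow-up period) and at the time of progression". For QLQ-C30 it says: "Assess every 6 weeks relative to first dose until end of study (including survival follow-up period) and at the time of progression". Table 2 continues both schedules after 24 months. Section 4.3.4 (Survival follow-up) introduces the same questionnaires with the words "the following assessments are also required post progression as detailed in the study plan". Table 9 in section 8.7.4 analyses PRO at the final data cut-off, at about 95 deaths, while RECIST endpoints stop at 24 months after the last subject's first dose.

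Other endpoints in 8.4 do say how next therapy is handled. For ORR, "any complete response or partial response which occurred after a further anticancer therapy was received will not be included in numerator of the ORR calculation". Best tumour shrinkage stops at progression or next therapy. Time to symptom deterioration says the opposite in terms: next therapy is disregarded. The improvement rate says neither.

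**The concern.** The secondary objective in section 2.2 is the impact of AZD9291 on symptoms and quality of life. A patient who never improves on AZD9291, stops, starts another drug and then reports less cough at two assessments is a symptom responder under this definition. A programmer following 8.4 would have to count that patient. There is no control arm in which the same thing happens, so the later drug's effect goes straight into the rate reported for AZD9291.

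Section 1.1 makes such relief plausible. It cites response rates of 20-30% for platinum chemotherapy after an EGFR-TKI, and section 8.2 expects 33% of patients to be chemotherapy-naïve at entry. Tumour response is not symptom relief, so these figures show only that a later drug may act. They do not measure the effect.

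Asking for consecutive or sustained improvement would not solve this, because a sustained improvement on later chemotherapy would still count.

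**Working it through.** The protocol states no expected improvement rate and no precision or power for it, so there is no figure to reproduce. The check is of the text, followed by an illustration.

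**Direction.** The denominator depends on the baseline score only. The numerator needs any two qualifying assessments. Adding later assessments can turn a non-improver into an improver but never the reverse, so the all-assessments rate is at least as high as the rate restricted to assessments before next therapy.

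**Opportunity.** On the three-weekly schedule alone (LC13 is weekly at first), 24 months of follow-up gives 24 × 30.44 / 21 = 34.8, about 35 LC13 assessments. The six-weekly QLQ-C30 gives 24 × 30.44 / 42 = 17.4, about 17. Any two that are 18 days or more apart can qualify.

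**Feasibility of a cut.** The date needed is already collected. A footnote to Table 1 reads: "Survival status including anti-cancer treatment to be performed every 6 weeks (relative to first dose) following disease progression or withdrawal from treatment".

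**Size, by assumption.** Let
- p = share with both qualifying assessments before next therapy, assumed 40-60%;
- s = share of the others who start a next therapy while PRO are still collected, assumed 30-70%;
- q = share of those who then reach a qualifying pair, assumed 10-30%.

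None of the three is in the protocol. The reported rate is p + (1 − p) × s × q, so the excess is (1 − p) × s × q.

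| p | s | q | Excess | Reported rate |
|---|---|---|---|---|
| 60% | 30% | 10% | 0.40 × 0.30 × 0.10 = 1.2 points | 61.2% |
| 50% | 50% | 20% | 0.50 × 0.50 × 0.20 = 5.0 points | 55.0% |
| 40% | 70% | 30% | 0.60 × 0.70 × 0.30 = 12.6 points | 52.6% |

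The first and last rows are the extremes of the assumed ranges: 1.2 to 12.6 points.

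**The case against.** **The SAP may set the window.** Section 8.1 promises a SAP, and which PRO records enter a descriptive table is often decided there. This does not dispose of the point. The protocol itself fixes the numerator rule, and for ORR and tumour shrinkage it puts the therapy cut in the same section.

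**Ignoring next therapy is a legitimate treatment-policy choice.** The nearest comparator, time to symptom deterioration on the same LC13 items, makes that choice openly, and so does PFS. This is the strongest argument. But the sentence covers only those endpoints. A responder rate also behaves differently: extra follow-up can only add responders, as with ORR, where the protocol bars it. What stands is that two LC13 endpoints would then follow different rules, and the protocol should say why.

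**The endpoint is secondary and descriptive**, with no threshold or decision attached. That is true, and it limits the weight of the point.

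**Collection may stop earlier for some.** Section 3.6.1 suggests that, for patients who stop AZD9291 without progression, PRO capture ends when RECIST assessments end. That sits badly with Table 1 and section 4.3.4. Even on that reading, scores after a new therapy started before progression would still count.

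**Conclusion.** The point holds for the symptom improvement rate. As written, improvement on a later drug counts, and it can only raise the figure attributed to AZD9291. The direction follows from the definition alone. The size, about 1 to 13 percentage points, rests wholly on the assumed p, s and q and cannot be fixed from the documents.

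Two stronger readings are not supported.

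- A reader might infer that the by-time-point summaries in section 8.7.2 also flatter AZD9291, since "the mean change from baseline scores at each time point will be summarised for all symptom scales/items from the QLQ LC13 and QLQ-C30" without a cut. Those summaries do mix treatments, but the direction is unknown: scores after progression may be worse and pull the means down. Filtering has its own bias, because later visits would then hold mainly patients still doing well on AZD9291.
- A reader might gauge the contamination by the share of follow-up that falls after progression. That is the wrong quantity. Sections 1.5 and 4.2 allow AZD9291 beyond RECIST progression, and some patients will start a new drug late or never.

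**What to change.** In section 8.4, count a patient as improved only if both qualifying assessments precede the start of the first subsequent anti-cancer therapy. Report the all-assessments rate as supportive.

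Leave time to symptom deterioration unchanged, and add a sentence saying why it disregards next therapy while the improvement rate does not. Keep the mean-change and improved/stable/worsened summaries on all data. A version restricted to assessments before next therapy may be added, as supportive only. PRO collection does not change, though section 3.6.1 should be reconciled with section 4.3.4 on how long it runs.

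The cost is small: a sentence or two in the protocol, one date filter on data already recorded, one extra table, and a slightly less favourable improvement rate.

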8.5 Calculation or derivation of safety variable(s)

Adverse events

Adverse Events (both in terms of MedDRA preferred terms and CTCAE grade) will be listed individually by patient.

Any AE occurring before treatment with AZD9291 will be included in the data listings but will not be included in the summary tables of AEs.

Any AE occurring within 28 days of discontinuation of investigational product (ie, the last dose of AZD9291) will be included in the AE summaries. Any events in this period that occur after a patient has received further therapy for cancer (following discontinuation of AZD9291) will be flagged in the data listings.

A separate data listing of AEs occurring more than 28 days after discontinuation of AZD9291 will be produced. These events will not be included in AE summaries

Other significant adverse events (OAEs)

During the evaluation of the AE data, an AstraZeneca medically qualified expert will review the list of AEs that were not reported as SAEs and AEs leading to discontinuation. Based on the expert's judgement, significant AEs of particular clinical importance may, after consultation with the Global Patient Safety Physician, be considered OAEs and reported as such in the CSR. A similar review of laboratory/vital signs/ECG data will be performed for identification of OAEs.

Examples of these could be marked haematological and other laboratory abnormalities, and certain events that lead to intervention (other than those already classified as serious), dose reduction or significant additional treatment.

Safety Assessments

For change from baseline summaries for vital signs, laboratory data, LVEF, ECGs and physical examination, the baseline value will be the latest result obtained prior to the start of investigational product.

The denominator used in laboratory summaries will only include evaluable patients, in other words those who had sufficient data to have the possibility of an abnormality.

For example:

- If a CTCAE criterion involves a change from baseline, evaluable patients would have both a pre-dose and at least 1 post-dose value recorded
- If a CTCAE criterion does not consider changes from baseline, to be evaluable the patient need only have 1 post dose-value recorded

The denominator in vital signs data should include only those patients with recorded data.

8.6 Calculation or derivation of health State utility (EQ-5D-5L)

The EQ-5D-5L index comprises 5 dimensions of health (mobility, self-care, usual activities, pain/discomfort and anxiety/depression). For each dimension, respondents select which statement best describes their health on that day from a possible 5 options of increasing levels of severity (no problems, slight problems, moderate problems, severe problems and unable to/extreme problems). A unique EQ-5D health state is referred to by a 5-digit code allowing for a total of 3125 health states. For example, state 11111 indicates no problems on any of the 5 dimensions. These data will be converted into a weighted health state index by applying scores from EQ5D value sets elicited from general population samples (the base case will be the United Kingdom valuation set, with other country value sets applied in scenario analyses). Where values sets are not available, the EQ-5D-5L to EQ-5D-3L crosswalk will be applied. In addition to the descriptive system, respondents also assess their health on the day of assessment on a visual analogue scale, ranging from 0 (worst imaginable health) to 100 (best imaginable health). This score is reported separately. The evaluable population will comprise the Full Analysis Set (FAS) population.

8.7 Methods for statistical analyses

All data will be presented for the overall full analysis set/evaluable for response set (as appropriate), and also by two cohorts defined by line of treatment; TKI treatment only / previous TKI and a platinum-based doublet chemotherapy (patients may have also received additional lines of treatment).

Descriptive statistics will be used for all variables, as appropriate. Continuous variables will be summarised by the number of observations, mean, standard deviation, median, minimum, and maximum. Categorical variables will be summarised by frequency counts and percentages for each category. Unless otherwise stated, percentages will be calculated out of the full analysis set.

Baseline will be the last assessment of the variable under consideration prior to the intake of the first dose of investigational product, except for efficacy variables. For efficacy variables, baseline is defined as the last visit prior to enrolment.

8.7.1 Analysis of the primary variable(s)

Objective response rate (ORR) by ICR in the evaluable for response analysis set will be presented together with 95% exact (Clopper Pearson) confidence intervals. Summaries of the number of patients with best response in each of the follow categories will be summarised: Complete Response (CR), Partial Response (PR), Stable Disease (SD), Progressive Disease (PD) and Non-Evaluable (NE).

The baseline patient characteristics will be summarised, including demographics, EGFR mutation type and prior anti-cancer therapy, including most recent previous treatment.

Additional summaries of ORR will be performed

- ORR by investigator assessment
- ORR summarised for both confirmed and unconfirmed responses
- ORR by EGFR mutation subtype: Exon 19 deletion/L858R/Other.
- ORR in the subgroup of patients who received TKI as last treatment prior to study start and those whose treatment prior to study start was not a TKI
- ORR at week 6 and 12 will also be summarised.

The concordance between ORR as assessed by ICR and by investigator will be presented.

